## **5 Statistical Analysis Sets**

### **5.1 Efficacy Analysis Set**

There are no efficacy analyses in this trial.

### **5.2 Safety Analysis Set**

All subjects who receive at least one dose of trial medication are included in the safety and demographic and baseline characteristic analyses.

### **5.3 Pharmacokinetic Analysis Set**

There are no pharmacokinetic analyses in this trial.

## **5.4 Pharmacodynamic Analysis Set**

Pharmacodynamic analyses will be conducted using the full analysis set (FAS) defined in the clinical trial protocol. All subjects who complete both periods of treatment with reference medication alone and treatment with reference medication and cilostazol are included in the pharmacodynamic analyses and demographic and baseline characteristic analyses.

## **5.5 Handling of Missing Data**

No data imputation will be performed for missing data in this trial.

# **6 Primary and Secondary Outcome Variables**

## **6.1 Primary Outcome Variables**

The primary analysis variable of the trial is ex-vivo inhibition of platelet aggregation (IPA).

- Ex-vivo platelet function: primary parameters to be determined in citrated platelet rich plasma (PRP) by
  - Light transmission aggregometry (5  $\mu$ M ADP, residual aggregation at 5 minutes)
  - Light transmission aggregometry (Arachidonic acid 500 mg/L, residual aggregation at 5 minutes)

For individual subjects, IPA is defined as the percentage decrease of platelet aggregation of stimulated plasma before and after treatments with trial medications.

$$\text{IPA (\%)} = 100 \times (\text{platelet aggregation at baseline} - \text{platelet aggregation after treatment}) / \text{platelet aggregation at baseline}$$

## **6.2 Secondary Outcome Variables**

- Skin bleeding time (BT): to be determined with Ivy method utilizing standardized bleeding with Surgicutt® device
- Ex-vivo platelet function as determined by
  - Light transmission aggregometry in PRP (20  $\mu$ M ADP, collagen 1 mg/L and 2.5 mg/L, TRAP 25  $\mu$ M residual aggregation at 5 minutes)
  - Multiple electrode impedance aggregometry in hirudine-anticoagulated blood (Multiplate®) (ASPI test, ADP test, ADP/PGE test, TRAP test)
  - VerifyNow™ (P2Y12 and Aspirin test)
  - Vasodilator-stimulated phosphoprotein (VASP) by flow cytometry

- P-Selectin expression by flow cytometry (ADP-stimulated, TRAP-stimulated, Unstimulated)

## **7 Disposition and Demographic Analysis**

### **7.1 Subject Disposition**

The number of subjects screened, treated, randomized to IMP, and completed the trial or withdrawn from the trial will be presented for screened subjects. The number and percentage of subjects withdrawn from the trial will be summarized by reason for withdrawal for treated subjects.

### **7.2 Demographic and Baseline Characteristics**

The descriptive statistics (mean, standard deviation, minimum, median, maximum) of age, height, body weight (at screening), and body mass index (BMI) will be calculated for each treatment group. The number and percentage of subjects for sex, race, ethnicity, and country will be summarized for each treatment group.

### **7.3 Medical History**

Medical history will be listed by subject.

### **7.4 Treatment Compliance**

Treatment compliance (name of treatment, start/end date of treatment, dose, route) will be listed by subject.

### **7.5 Prior and Concomitant Medication**

Concomitant medications will be summarized by World Health Organization Drug Dictionary (WHO-DD) (March 2015) anatomical therapeutic chemical (ATC) classification and preferred name for each treatment group.

### **7.6 Protocol Deviations**

Not applicable

## 8 Efficacy Analyses

Not applicable

## 9 Safety Analyses

### 9.1 Extent of Exposure

The number and percentage of subjects will be summarized according to the duration of exposure (end date of each treatment – start date of each treatment + 1) to investigational medicinal product (IMP) for each treatment group.

### 9.2 Adverse Events

Treatment-emergent adverse events (TEAEs) are defined as adverse events (AEs) that occurred after the start of IMP administration. TEAEs by treatment regimen are classified as below:

- TEAEs for cilostazol alone: TEAEs that occurred from the start of IMP administration in Period A until the start of IMP administration in Period C
- TEAEs for the reference medication alone: TEAEs that occurred from the start of IMP administration in Period C until the start of IMP administration in Period D
- TEAEs for the reference medication and cilostazol: TEAEs that occurred after the start of IMP administration in Period D

All adverse events will be coded by Medical Dictionary for Regulatory Activities (version 20.0) system organ class and preferred term. The incidence of the following events will be summarized by treatment group and by treatment regimen:

- Treatment-emergent AEs (TEAEs)
- TEAEs by severity
- TEAEs with an outcome of death
- Serious TEAEs
- TEAEs leading to discontinuations of the IMP

TEAEs causally related to the IMP (“Related”, “Possibly related” or “Unlikely related”) will be summarized in the same manner. If multiple occurrences of the same event are observed in the same subject during the same treatment regimen, the occurrence with the highest severity will be used for all analyses.

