## 2 Trial Objectives

The primary objective of this trial is to determine the effects of orally administered cilostazol 100 mg twice daily, Acetylsalicylic acid (ASA) 100 mg once daily or clopidogrel 75 mg once daily alone as well as in combination of cilostazol 100 mg twice daily/ clopidogrel 75 mg once daily or cilostazol 100 mg twice daily/ ASA 100 mg once daily on ex-vivo platelet function testing.

A key secondary objective is the effect of orally administered cilostazol 100 mg twice daily, ASA 100 mg once daily or clopidogrel 75 mg once daily alone as well as in combination of Cilostazol 100 mg twice daily/ clopidogrel 75 mg once daily or cilostazol 100 mg twice daily/ ASA 100 mg once daily on bleeding time in healthy subjects. While bleeding time is an important parameter in this regard it also does exhibit a higher level of intra- as well as interindividual variability and an additional tissue dependent variability. Therefore, bleeding time is evaluated as a key secondary parameter.

In addition, the effects of a combined administration of cilostazol 100 mg twice daily/ clopidogrel 75 mg once daily in subjects with a homozygous wildtype allele of *CYP2C19* (\*1/\*1) showing normal *CYP2C19* activity will be compared with the effects of subjects carrying either the heterozygous *CYP2C19* (\*1/\*2) isoform and with subjects carrying the homozygous *CYP2C19* (\*2/\*2) isoforms, displaying a intermediate and poor *CYP2C19* activity, respectively.

A further secondary objective is to assess the safety variables after the orally administration of cilostazol 100 mg twice daily, ASA 100 mg once daily or clopidogrel 75 mg once daily alone as well as a combination of cilostazol 100 mg twice daily/ clopidogrel 75 mg once daily or cilostazol 100 mg twice daily/ ASA 100 mg once daily.

[figure not shown]

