**Appendix 1                      List of Summary Tables**

- CT-1 Subject Disposition
- CT-2 Reasons for Discontinuation
- CT-3.1 Demographic and Baseline Characteristics - Safety Analysis Set
- CT-3.2 Demographic and Baseline Characteristics - Pharmacodynamic Analysis Set
- CT-4 Concomitant Medications
- CT-5.1 Summary of Pharmacodynamic Parameters
- CT-5.2 Summary of Pharmacodynamic Parameters by Genotype
- CT-5.3 Descriptive Statistics for Inhibition of Platelet Aggregation
- CT-5.4 Descriptive Statistics for Skin Bleeding Time
- CT-5.5 Treatment Difference for Inhibition of Platelet Aggregation
- CT-5.6 Treatment Difference for Inhibition of Platelet Aggregation by Genotype
- CT-5.7 Descriptive Statistics for Platelet Aggregation
- CT-6.1 Summary of Pharmacodynamic Parameters - Exploratory Analysis (not Log-transformed Data)
- CT-6.2 Summary of Pharmacodynamic Parameters by Genotype - Exploratory Analysis (not Log-transformed Data)
- CT-7 Extent of Exposure to Investigational Medicinal Product
- CT-8.1 Summary of Adverse Events
  - CT-8.2.1 Incidence of All Treatment-emergent Adverse Events by MedDRA System Organ Class and Preferred Term for Each Treatment Group
  - CT-8.2.2 Incidence of All Treatment-emergent Adverse Events by MedDRA System Organ Class and Preferred Term for Each Treatment Regimen
  - CT-8.3.1 Incidence of Potentially Drug-related Treatment-emergent Adverse Events by MedDRA System Organ Class and Preferred Term for Each Treatment Group
  - CT-8.3.2 Incidence of Potentially Drug-related Treatment-emergent Adverse Events by MedDRA System Organ Class and Preferred Term for Each Treatment Regimen
  - CT-8.4.1 Incidence of Serious Treatment-emergent Adverse Events by MedDRA System Organ Class and Preferred Term for Each Treatment Group

Protocol 21-13-102

CT-8.4.2 Incidence of Serious Treatment-emergent Adverse Events by MedDRA System Organ Class and Preferred Term for Each Treatment Regimen

CT-8.5.1 Incidence of Treatment-emergent Adverse Events Leading to Discontinuation of Investigational Medicinal Product Administration by MedDRA System Organ Class and Preferred Term for Each Treatment Group

CT-8.5.2 Incidence of Treatment-emergent Adverse Events Leading to Discontinuation of Investigational Medicinal Product Administration by MedDRA System Organ Class and Preferred Term for Each Treatment Regimen

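### As written, the adverse event tables by regimen combine ASA with clopidogrel, so four of the five regimens in the safety objective have no incidence column of their own

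*SAP*

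**What the plan says.** Section 2 introduces the safety objective with "A further secondary objective is to assess the safety variables after the orally administration of cilostazol 100 mg twice daily, ASA 100 mg once daily" and goes on to clopidogrel alone and to cilostazol combined with clopidogrel or with ASA. That makes five regimens.

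Under Section 3.2 every subject takes cilostazol in Period A and washes out in Period B. In Period C, Group 1 takes ASA and Groups 2, 3 and 4 take clopidogrel. In Period D all groups add cilostazol. Each group is planned at 17 subjects.

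Section 9.2 counts any adverse event after the first dose of IMP as treatment-emergent and assigns these events to three regimens:

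- The first spans Period A and the wash-out: "TEAEs for cilostazol alone: TEAEs that occurred from the start of IMP administration in Period A until the start of IMP administration in Period C".
- The second closes when Period D dosing begins, and its definition opens with "TEAEs for the reference medication alone: TEAEs that occurred from the start of IMP administration in Period C".
- The third has no stated end: "TEAEs for the reference medication and cilostazol: TEAEs that occurred after the start of IMP administration in Period D".

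Incidence is then summarised by treatment group and by treatment regimen. Appendix 1 lists the two as separate tables. The group version, CT-8.2.1, is titled "Incidence of All Treatment-emergent Adverse Events by MedDRA System Organ Class and Preferred Term for Each Treatment Group", while the regimen version, CT-8.2.2, is titled "Incidence of All Treatment-emergent Adverse Events by MedDRA System Organ Class and Preferred Term for Each Treatment Regimen". The same pairing runs through CT-8.3 to CT-8.6.

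**The concern.** The three regimens are set by period boundaries alone. Because the Period C drug depends on the group, a column built on the Period C or Period D window takes in subjects on two different drugs. The tables that do keep the groups apart have the opposite limitation: they carry no period limit, so a Group 1 incidence includes events from Periods A and B, before any ASA was taken.

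What is at stake is whether a reader of the report can see the adverse event incidence on ASA, on clopidogrel, and on each of them with cilostazol added. Adding cilostazol to each drug is the comparison the trial is built around, and Section 11.1.1 names the two drug pairs separately for the pharmacodynamic analysis. Section 9.2 has no matching statement for adverse events.

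**Working it through.** The SAP gives no figure to reproduce here. The check sets the objective against the specified tables and then shows what pooling does to an incidence.

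**Step 1: who is in each column (Section 3.2).** ASA: Group 1, 17 subjects. Clopidogrel: Groups 2, 3 and 4, 3 × 17 = 51. (The Group 4 bullet carries the label Group 3 in its bracket. I read this as a slip, since 68 − 3 × 17 = 17.) Total 17 + 51 = 68, with shares 17/68 = 25% and 51/68 = 75%.

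**Step 2: objective against tables.**

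| Regimen in Section 2 | Regimen in Section 9.2 that holds it | Own column in the regimen tables? |
|---|---|---|
| Cilostazol alone (68) | Cilostazol alone | Yes |
| ASA alone (17) | Reference alone | No, combined with clopidogrel |
| Clopidogrel alone (51) | Reference alone | No, combined with ASA |
| Cilostazol + ASA (17) | Reference + cilostazol | No, combined with cilostazol + clopidogrel |
| Cilostazol + clopidogrel (51) | Reference + cilostazol | No, combined with cilostazol + ASA |

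Four of the five regimens share a column.

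**Step 3: what a shared column reports.** Pooled incidence = (17 × p_ASA + 51 × p_clopidogrel) / 68 = 0.25 × p_ASA + 0.75 × p_clopidogrel. All event rates below are assumed.

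- 5/17 = 29.4% and 3/51 = 5.9% give (5 + 3)/68 = 11.8%.
- 30% and 10% give 0.25 × 30% + 0.75 × 10% = 15%.
- 40% and 0% give 10%, the same as 10% on both drugs.
- In reverse, a reported 10/68 is compatible with 0/17 and 10/51 (0% against 19.6%), with 10/17 and 0/51 (58.8% against 0%), and with anything between.

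**Step 4: can the by-group tables undo the pooling?** In the by-group tables, Group 1 contributes four planned weeks (A to D). Weeks A and B precede any ASA, week C is ASA alone, and week D is ASA with cilostazol. So ASA is taken in two of the four weeks.

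Take the simplest case, in which no subject has the event in more than one period. The unknown counts form a table of 2 drugs × 3 regimens. The by-group tables give its row totals and the by-regimen tables its column totals. That leaves (2 − 1) × (3 − 1) = 2 cells free, so in general the drug-specific counts are not determined. If a subject has the same event in two periods, a by-group count of subjects no longer equals the sum across regimens, and recovery is harder still.

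**The case against.** The SAP nowhere says in words that ASA and clopidogrel events will be combined. The three definitions in Section 9.2 can be read as time windows, with the reference medication meaning each subject's own drug. Applied with the group allocation, they would yield exactly the five regimens of Section 2. Section 11.1.1 supports that reading, because it names both drug pairs after using Test and Reference generically. Appendix 1 gives titles only, the table shells are not shown, and CT-8.1 states no split, so five columns are not excluded.

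This lowers the confidence but does not remove the point. The drug-specific reading is spelled out for the pharmacodynamic comparisons and not for adverse events. Where the SAP wants an extra split it puts it in the title, as with the genotype tables CT-5.2, CT-5.6 and CT-6.2, and no adverse event table has such a title. A programmer following Section 9.2 literally would build three classes.

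A reader might go further and infer that the safety objective cannot be answered at all. The documents do not support that. The objective covers safety variables generally. Sections 9.3 to 9.5 summarise laboratory values, vital signs and body weight by treatment group at each timepoint, which keeps ASA apart from clopidogrel. Listing AE-1 and CT-9.1 to CT-9.3 give subject-level event data. The by-group incidence tables also retain some contrast: Groups 1 and 2 are both wildtype and share the cilostazol week, so that week dilutes a difference between ASA and clopidogrel without erasing it.

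**Conclusion.** The point stands as a gap in the specified adverse event incidence tables. As written, two of the three regimen columns combine 17 subjects on ASA with 51 on clopidogrel, and no listed table separates them by period. Four of the five regimens in the safety objective therefore have no incidence column of their own.

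This rests on reading the reference medication in Section 9.2 as one category, on the planned group sizes, and on the table titles without their shells. Confidence is moderate for that reason. The illustrative event rates are assumptions; only the 25:75 mix comes from the SAP.

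It should be fixed, but it does not call for the highest grade. The tables are descriptive, they serve a further secondary objective, and the primary pharmacodynamic analysis is unaffected.

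**What to change.** In Section 9.2, do one of two things:

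- Define five TEAE regimens: cilostazol alone, ASA alone, clopidogrel alone, cilostazol plus ASA, and cilostazol plus clopidogrel. Planned denominators are 68, 17, 51, 17 and 51.
- Keep the three time windows but state that the regimen tables are produced within each treatment group. Each cell then has a planned denominator of 17, and the clopidogrel total is the sum over Groups 2 to 4.

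Produce CT-8.2.2, CT-8.3.2, CT-8.4.2, CT-8.5.2 and CT-8.6.2 on that basis, with subjects actually dosed in the relevant period as denominator. If drug-specific columns were always intended, one sentence saying so, plus the denominator rule, is enough.

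The cost is SAP wording and some extra columns in tables already planned, with no new data. The only downside is that some columns have small denominators.

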CT-8.6.1 Incidence of All Treatment-emergent Adverse Events According to Severity by MedDRA System Organ Class and Preferred Term for Each Treatment Group

CT-8.6.2 Incidence of All Treatment-emergent Adverse Events According to Severity by MedDRA System Organ Class and Preferred Term for Each Treatment Regimen

CT-9.1 Listing of Deaths

CT-9.2 Listing of Serious Adverse Events Other Than Deaths

CT-9.3 Listing of Adverse Events Leading to Discontinuation of Investigational Medicinal Product Administration

CT-10.1.1 Descriptive Statistics for Laboratory Test Results - Serum Chemistry

CT-10.1.2 Descriptive Statistics for Laboratory Test Results - Hematology and Coagulation

CT-10.1.3 Descriptive Statistics for Laboratory Test Results - Urinalysis

CT-10.2.1 Shift Table of Laboratory Test Results - Serum Chemistry

CT-10.2.2 Shift Table of Laboratory Test Results - Hematology and Coagulation

CT-10.2.3 Shift Table of Laboratory Test Results - Urinalysis

CT-10.3.1 Shift Table of Laboratory Test Results - Qualitative Urinalysis (1)

CT-10.3.2 Shift Table of Laboratory Test Results - Qualitative Urinalysis (2)

CT-10.4 Listing of Abnormal Laboratory Findings

CT-10.5 Listing of Potential Hy's Law Cases

CT-11.1 Descriptive Statistics for Vital Signs

CT-11.2 Descriptive Statistics for Body Weight

CT-12 Shift Table of Electrocardiogram Findings

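### Keeping only the most severe repeat of an adverse event for all analyses can drop a subject from the related, serious and discontinuation tables, and the rule does not cover the treatment-group severity table

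*SAP*

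**What the plan says.** Section 9.2 of the SAP sets out the adverse event summaries: all treatment-emergent events, events by severity, fatal events, serious events, and "TEAEs leading to discontinuations of the IMP". Events in the SAP's related categories "will be summarized in the same manner". On the level of tabulation it says: "The incidence of the following events will be summarized by treatment group and by treatment regimen". Appendix 1 follows this with paired tables, CT-8.2.1/8.2.2 to CT-8.6.1/8.6.2, the first of each pair by treatment group and the second by regimen.

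Three regimens are defined for each subject: cilostazol alone, reference medication alone, and the combination from the start of Period D.

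There is one rule for repeats. Its condition is "If multiple occurrences of the same event are observed in the same subject during the same treatment regimen", and its consequence is that "during the same treatment regimen, the occurrence with the highest severity will be used for all analyses". The section does not say whether a table's criterion is applied before or after repeats are collapsed, which occurrence is kept when severities tie, or what happens to repeats in different regimens. It does not define incidence.

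**The concern.** Severity, seriousness, relationship to treatment and action taken are separate attributes of an adverse event record. A rule that picks one record on severity and uses it everywhere can discard the record that places the subject in another table. The tables exposed are those for related, serious and discontinuation events, which readers consult first for safety. Two programmers could also produce different tables from the same data, one by filtering first and the other by collapsing first.

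The second problem is one of level. Half of the tables are by treatment group and span all regimens, but the rule stops at the regimen boundary. Every subject takes cilostazol in Period A and again in Period D (Section 3.2), so the same event can be expected to recur across regimens in some subjects. Nothing says which severity then represents the subject in the group table.

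**Working it through.** The SAP gives no figure on this point, so there is none to reproduce. The check applies the rule as written.

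**Inputs.** The repeat rule, table criteria and regimens come from Section 9.2, the table list from Appendix 1, and 17 subjects per group from Section 3.2. A three-grade severity scale is assumed, because Section 9.2 does not name the grades.

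**Step 1: two occurrences in one subject and one regimen.** Give each occurrence a severity (3 grades) and a yes/no flag for the table's criterion (related, serious, or led to discontinuation).

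- Configurations: 3 × 3 × 2 × 2 = 36.
- With neither occurrence flagged: 3 × 3 = 9. With at least one flagged: 36 − 9 = 27.
- Both flagged: 9. The subject stays in the table.
- Exactly one flagged: 27 − 9 = 18. In 6 the flagged occurrence is the more severe and is kept. In 6 it is the less severe and is dropped. In 6 the severities tie and the rule does not say which is kept.

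The rule therefore loses 6 of 27 configurations and leaves 6 undetermined. These are counts of possibilities, not probabilities. No configuration adds a subject who does not qualify, so at regimen level the error runs only downwards.

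Example: in Period C a subject has a moderate headache outside the related categories and a mild headache rated related. Only the moderate one is kept, and the subject is missing from CT-8.3.2 for headache. The subject is also missing from CT-8.3.1 unless a qualifying headache is kept from another regimen.

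**Step 2: weight of one subject.** 1/17 = 5.9 percentage points of a treatment group. The safety set (Section 5.2) takes everyone dosed, including subjects later replaced, so the denominator may be larger. With the two replacements foreseen for Group 3 or Group 4 it is 1/19 = 5.3 points. If a regimen column pools all 68 subjects, it is 1/68 = 1.5 points.

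**Step 3: the same event in different regimens.** Take one subject with the event mild in Period A, moderate in Period C and severe in Period D. The rule collapses nothing, since each occurrence is alone in its regimen. Three records remain, and in CT-8.6.1 the subject falls in three severity rows. Added over rows, this is 3/17 = 17.6% where one subject is 1/17 = 5.9%. With two different severities it is 2/17 = 11.8%. At the extreme, the rows for one event in one group could add to 3 × 17 = 51 entries for 17 subjects.

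**Step 4: the other group tables.** If incidence counts subjects with at least one event, this subject counts once in each of CT-8.2.1 to CT-8.5.1 for which a kept record qualifies, however many records remain. Duplicates across regimens do not change those tables.

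**Step 5: the proposed rule.** If the criterion is applied first, 0 of the 27 configurations are lost. If maximum severity is taken over the whole column, each subject falls in one row of CT-8.6.1 per event, at most 17 per group.

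**The case against.** The strongest reply has four parts.

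- **The coincidence is narrow.** The same subject must have the same event at least twice in one regimen, with the qualifying occurrence milder or tied. Treatment periods last one week, although the cilostazol-alone window also takes in the wash-out. For relatedness, the SAP's category includes events rated unlikely related, so only a more severe occurrence outside all three categories can displace a qualifying one. This stands. The repeated use of cilostazol in Periods A and D does not weaken it, because that concerns recurrence across regimens.
- **The events remain visible.** Deaths, other serious events and events leading to discontinuation have their own listings (CT-9.1 to CT-9.3), and AE-1 lists adverse events. This stands too. A reader might infer that such events vanish from the report, and the documents do not support that. The loss is in the incidence tables. Related events, however, have no dedicated listing in the CT-9 series.
- **A programmer could filter first.** The SAP fixes no order of steps, so this is possible. But the rule says the selected occurrence serves all analyses, which points the other way.
- **Incidence ordinarily counts subjects.** This stands and limits the second part of the point. A reader might infer that every treatment-group table is inflated, or might size the inflation by adding assumed event rates for Periods A and D. That would count records. The SAP nowhere says that records are the numerator, and it gives no event rates. Under subject counting only CT-8.6.1 is affected.

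**Conclusion.** The point holds within limits. Taken literally, the repeat rule in Section 9.2 can understate the related, serious and discontinuation incidence tables, and it leaves ties in severity undecided. At regimen level it can never overstate them. One lost subject is worth 5.9 points in a group of 17, but that is the weight of a subject and not an estimate of the effect. How often a loss would occur cannot be derived from the SAP.

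The rule also leaves the group severity table CT-8.6.1 without a rule across regimens, so one subject can fall in two or three of its rows. That CT-8.2.1 to CT-8.5.1 are free of duplicates rests on incidence meaning subjects with at least one event, which is the ordinary reading but is not stated.

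The primary pharmacodynamic analysis is untouched. The case for a correction is that a stated rule gives the wrong result in safety tables and is cheap to put right.

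**What to change.** Replace the sentence on repeated occurrences in Section 9.2 with:

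> In each table a subject is counted once per preferred term and column if any occurrence meets the table's criterion (related, serious, leading to discontinuation); only in the severity tables is the maximum severity taken, over all qualifying occurrences in that column (the regimen, or all periods for treatment-group tables).

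This settles the order of steps, makes ties irrelevant, states that incidence counts subjects, and gives CT-8.6.1 its own level. The cost is one sentence in the SAP and a change in the order of programming steps. No new data are needed.
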